7. METHODS

a. Study parameters/endpoints

i. Main study parameter/endpoint

Primary parameters and endpoints

Evaluation of the implementation of a continuous monitoring method on the surgical ward

- Fidelity: The usability and degree of implementation of the Healthdot at the surgical ward
 - Measured with the System usability scale (SUS), Score > 68 at M6 (8, 26)

- Acceptability: The workload regarding the amount of spot checks in addition to the standard monitoring.
 - Calculated with data from the electronic patient file records. Success in case of average reduction of 20% at M6 compared to M3

ii. Secondary study parameters/endpoints (if applicable)

Secondary parameter and endpoints

- Adoption: The intention and attitude towards the use of the Healthdot monitoring method.
 - Measured with evidence-based practise attitude scale (EBPAS) (9, 10).
- Feasibility: The extent to which the Healthdot monitoring method can be successfully carried out by the healthcare employees.
 - Measured with a thematic analysis (Braun and Clark) with core group (11).
- Acceptability: Amount of manual spot checks per hospital admission day per patient
 - \circ Calculated with data from the electronic patient file records.
- Acceptability: The perception among nursing staff given the satisfactory and agreeableness regarding workload.
 - Measured with the integrated workload scale (IWS) (12, 13).
- Appropriateness: Relation between device false alarms (noise) and correct alarms based on the alarming protocol.
 - Measured as signal to noise ratio (SNR)
- Appropriateness: Number of unexpected events that occur during or result from the use of the Healthdot medical device. Measured as adverse device events (ADE)
- Feasibility: The amount of time needed to perform and process a complete manual spot check or digital monitoring check. Measured manually.
- Costs: Cost-effectiveness analysis based on the duration of admission, the associated admission costs and the monitoring method
- Advanced algorithm analyses for improved monitoring protocols with advanced AI software

iii. Other study parameters (if applicable)

Additional anonymized data will, in case of informed consent, be collected from the electronic patient file such age, gender, reason for admission, medical history, duration of admission, complications and laboratory results. This additional data will be used to relate the primary and secondary results to any influencing factors/ baseline characteristics and potentially correct for these factors.

Variables eCRF

Characteristic	Input
Indication	Open
Type of invasive interventions/surgery	Open
Gender	M/F
Age	Open
BMI	Kg/m2
Comorbidities	
Charlson comorbidity index	Charlson Comorbidity Index (CCI) - MDCalc
Hospital stay	
Admission date	D/M/Y
Discharge date	D/M/Y
Elective or emergency	Open
Complications	
Clavien-Dindo classification	Grade I-V
Complications type	Cardiac, Pulmonary, Kidney failure,
	infectious, traumatic, surgical related
	(perforation, leakage, bleeding)
Urgent consultations (SIT) during	0-99
hospitalization	
ICU admission	Yes/no
Mortality <30 days	Yes/no
Re-admission < 30 days	Yes/no
Fidelity	
Total minutes monitored	Min
Amount of heart rate measurements	Total number per admission
Amount of respiratory rate measurements	Total number per admission
Artefact heart rate measurements	Total number per admission
Artefact respiratory rate measurements	Total number per admission
Total amount of spot checks	Total number per admission
Device	
Premature removal of device	Yes/no
Replacement of device	Yes/no
Bijzonderheden device	Yes/no

b. Randomisation, blinding and treatment allocation

N/A

c. Project procedures

Prior to the start of the pre-implementation phase there will be a pre-implementation phase during months 1-2. This phase will consist of training the medical staff through e-learning and physical meetings. During this phase, medical staff will have the opportunity to apply the Healthdot, learn to activate it and practise with the Guardian dashboard. This phase serves as preparation for the implementation and aims to optimize the intra-structure in advance. In addition, during this phase, baseline data will be collected about the standard spot check measurements, feeling of confidence and attitude towards a change in the monitoring method. This study is a quality project and a change in standard of care. Nurses and physicians voluntarily participating in the focus group will sign informed consent for participation. Nurses not participating in the focus group but working at the surgical ward during this project will

During the first phase, the daily output will consist of:

• 3x daily spot check according to the hospital protocol where the vital values are manually entered in the electronic patient file and scored with EWS. In addition, the Healthdot will be applied for training purposes. Data from the Healthdot during this phase will not be used in clinical care.

Alarmsignalen bij vitaal bedreigde patiënt 2							
EWS Score	3	2	1	0	1	2	3
Hartfrequentie		<40	40-50	51-100	101-110	111-130	>130
Bloeddruk (syst)	<70	70-80	81-100	101-200		>200	
Ademfrequentie		<9		9-14	15-20	21-30	>30
Temperatuur		<35,1	35,1-36,5	36,6-37,5	>37,5		
Bewustzijn				Α	v	Р	U
A = Alert V = Reactie op aanspreken P = Reactie op pijn U = Geen reactie							
Wanneer u ongerust bent over de conditie van de patiënt: I punt extra							
Wanneer de urineproductie <75 ml gedurende de afgelopen 4 uur: I punt extra SIT:							
Indien de saturatie <	90 ondanks	therapie: ->	3 punten			sein 1	[name]

Table 2: Current (M)EWS protocol at the Catharina hospital for ward monitoring

During phase 2, the Healthdot is the primary monitoring method. Each patient admitted to the surgical ward will receive the Healthdot during intake until discharge. In case the hospitalization duration is longer than the battery life, approximately 14 days, the Healthdot will be replaced by a new device. The Healthdot measures heart rate, respiration rate and physical activity every 5 minutes. These parameters are displayed in the Guardian dashboard as a trendline and automatically transferred to the electronic patient file 3 times a day (08u,12u,17u). These measurements are scored in accordance with the alarm protocol and, if necessary, provide a notification. In case of an additional measurement, a spot check will be performed by the nursing staff.

The protocol alarms in case the respiration rate is above 20/min and or the heart rate is 110 or more for 15 minutes consecutive.

Score	0	+1	+2] [CREWS	
Vital parameter							
Heart rate	<110		≥110		0-1	2	3
Respiration rate	<20	≥20					

Table 3: New CREWS protocol for monitoring with Healhtdot on the ward

Indications for spot check monitoring

- Based on previous research, the Healthdot measurements can be relied upon, and no additional spot check monitoring will be routinely necessary for respiration and heart rate unless clinical doubt about the obtained value.
- Additional spot check monitoring for blood pressure, oxygen saturation and temperature may be requested by any member of the treatment team

Premature termination of the study

• In the event that the International Workload Scale (IWS) (13) is in the highest category at moment 4-5 for more than 50% of the staff.

d. Withdrawal of individual subjects

Subjects of the core group can leave the study at any time for any reason if they wish to do so without any consequences.

i. Replacement of individual subjects after withdrawal

Participants who withdraw their participation from the core group won't be replaced.

e. Follow-up of subjects withdrawn from treatment

N/A

f. Premature termination of the study

In case the International Workload Scale (IWS) will be in the highest category of this scale for more than 50% of the staff at month 4-5 during phase two of this project.

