Healthcare has undergone major development in recent decades due to the application of new technology. One of these developments concerns the monitoring of in-hospital admitted patients and remote monitoring of discharged patients with smart autonomous sensors (1). This technological development is highly desirable as the current manually performed monitoring is sub-optimal and has not undergone major development, unlike prevention, diagnosis and treatment, since the 90's (2). Hospital care is currently in a transitional phase, which has been accelerated by the COVID-19 pandemic, to more outpatient care, shortened length of admissions and single day admission. The demographics of the hospitalized patients have therefore changed to a more vulnerable and comorbid population which makes them more prone for complications (3). On addition, the health care sector experiences staff shortages, especially within nursing care while the demand for hospital care expands. As a result, the workload is high, time is scarce and quality of care can be negatively influenced (4). Monitoring is according to current hospital protocol manually measured, three times a day and displayed as EWS score. This method is time-consuming, inefficient, subjective and error prone (3). Smart autonomous sensors have the potential, illustrated in previous research and literature, to cope with these challenges (5). However, implementation and integration of a new system is complex and must be carried out step by step with all those involved (6).

This study aims to step-by-step implement and evaluate an already validated smart monitoring device, the Philips Healthdot, on a hospital ward at the Catharina hospital.

Rationale: Ward monitoring is crucial in early recognition of complications and clinical deterioration. Smart autonomous monitoring enables continuous observation, is expected to reduce nursing workload, improve efficiency without compromise in confidence and might cause earlier recognition of clinical decline.

Objective:

Primary objectives

Evaluation of the implementation of a continuous monitoring method on the surgical ward

- The degree to which the Healthdot monitoring method is implemented as originally planned
- Average amount of manual spot checks per hospital admission day

Secondary objectives

• The intention and attitude towards the use of the Healthdot monitoring method.

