The medical research council (MRC) provided a document in 2000, the MRC model, to help researchers use the correct research designs, methods and measuring instruments (6). This model was revised in 2021 and forms the basis of the design of this project (6). This model structures the analysis using psychometric properties such as: acceptability, adoption, appropriateness, costs, feasibility, fidelity, penetration and sustainability (7).

Primary endpoints

Evaluation of the implementation of a continuous monitoring method on the surgical ward

- Fidelity: The usability and degree of implementation of the Healthdot at the surgical ward. Measured with the System usability scale (SUS), Score > 68 at M6 (8)
- Acceptability: The workload regarding the amount of spot checks in addition to the standard monitoring. Calculated with data from the electronic patient file records.
 Success in case of average reduction of 20% at M6 compared to M3

Secondary endpoints

- Adoption: The intention and attitude towards the use of the Healthdot monitoring method. Measured with evidence-based practise attitude scale (EBPAS)(9, 10).
- Feasibility: The extent to which the Healthdot monitoring method can be successfully carried out by the healthcare employees. Measured with a thematic analysis and input from the core group (Braun and Clark)(11)
- Acceptability: The workload regarding the amount of spot checks per hospital admission day per patient. Calculated with data from the electronic patient file records.
- Acceptability: The perception among nursing staff given the satisfactory and agreeableness regarding workload. Measured with the integrated workload scale (IWS) (12, 13).
- Appropriateness: Relation between device false alarms (noise) and correct alarms based on the alarming protocol. Measured as signal to noise ratio (SNR)
- Appropriateness: Number of unexpected events that occur during or result from the use of the Healthdot medical device. Measured as adverse device events (ADE)
- Feasibility: The amount of time needed to perform and process a complete manual spot check or digital monitoring check. Measured by manual time measurement.
- Costs: Cost-effectiveness analysis based on the duration of admission, the associated admission costs and the monitoring method. Calculation based on provided care and associated costs
- Algorithm improvement: Advanced algorithm analyses for improved monitoring protocols with use of artificial intelligence (AI)

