2. OBJECTIVES

Objective:

Primary objectives

Evaluation of the implementation of a continuous monitoring method on the surgical ward

- Fidelity: The usability and degree of implementation of the Healthdot at the surgical ward
- Acceptability: The workload regarding the amount of spot checks in addition to the standard monitoring.

Secondary objectives

- Adoption: The intention and attitude towards the use of the Healthdot monitoring method.
- Feasibility: The extent to which the Healthdot monitoring method can be successfully carried out by the healthcare employees
- Acceptability: The workload regarding the amount of spot checks per hospital admission day per patient
- Acceptability: The perception among nursing staff given the satisfactory and agreeableness regarding workload.
- Appropriateness: Relation between device false alarms (noise) and correct alarms based on the alarming protocol.
- Appropriateness: Number of unexpected events that occur during or result from the use of the Healthdot medical device.
- Feasibility: The amount of time needed to perform and process a complete manual spot check or digital monitoring check.
- Costs: Cost-effectiveness analysis based on the duration of admission, the associated admission costs and the monitoring method
- Advanced algorithm analyses for improved monitoring protocols

Primary hypothesis:

Previous own research (TRICA-trial, PEACH-trial) (15, 17) has shown that the Healthdot monitoring device is non-inferior to manual monitoring with EWS on the surgical ward regarding predicting and alarming of deteriorating patients based on vital parameter alterations. Our hypothesis is that implementation of this new monitoring method is a challenge but that a stepwise and careful approach, with involvement of all healthcare staff, will have a positive effect on the nursing workload and efficiency without reduction in

confidence and thereby improvement of the overall workability and efficiency at the surgical ward.

Secondary hypothesis:

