8. STATISTICAL ANALYSIS

The statistical analysis at professional (nurses/ physicians) level will be performed by means of descriptive statistics. Each continuous parameter is analyzed for normality by the Shapiro-Wilk test and visually by a figure. Normality-based reporting will be done using medians and interquartile ranges (IQR) or means and standard deviations (SD). Frequencies and percentages are reported for categorical data. Each continuous parameter is checked for normality by the Shapiro-Wilk test and visually by a figure. Normality-based reporting will be a figure. Normality-based reporting is performed using medians and interquartile ranges (IQR) or means and standard deviations (SD).

All analysis are performed using IBM SPSS Statistics 26.0 for Windows (IBM Armork, New York, USA) with 95% confidence interval and p < .05 as statistically significant.

The core group consisting of nurses, physicians and investigators will conduct a structured analysis into the fidelity, feasibility and acceptance of the implementation and this information is processed and objectified by means of a Braun and Clarke thematic analysis.

Objective	Instrument	Variable	Statistical test
Fidelity	SUS ^p	Continuous	Unpaired T-test/ Mann- Whitney U test
Acceptance	SC/day ^p SC/patient ^s IWS ^s	Continuous Continuous Ordinal	Descriptive statistics Descriptive statistics One-way ANOVA test
Adoption	EBPAS ^s	Continuous	Repeated measures ANOVA
Appropriateness	SNR ^s ADE ^s	Continuous Continuous	Descriptive statistics Descriptive statistics
Feasibility	Thematic analysis ^s	Nominal	Braun & Clarke thematic analysis
Time efficiency	Time measurement	Continuous	Descriptive statistics
Costs	Evaluation	Continuous	Descriptive statistics

Table 4: psychometric properties and statistical analysis

a. Other study parameters

N/A

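### Fidelity is judged only by a usability score: its degree-of-implementation half has no measure, so it could be declared met at any level of device use

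*Combined protocol and SAP*

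**What the plan says.** - **Objective.** The Summary gives the first primary objective as "The degree to which the Healthdot monitoring method is implemented as originally planned". Section 2 words it as "Fidelity: The usability and degree of implementation of the Healthdot at the surgical ward", and the Summary endpoint list and section 7.a.i use the same two-part definition.
- **Success rule.** Section 7.a.i: "Measured with the System usability scale (SUS), Score > 68 at M6". The Summary gives the same rule. No second criterion is attached to fidelity.
- **Timetable and analysis.** In the measurement timetable (Table 2, section 3) SUS is the only Fidelity instrument, taken at months 4 and 6. In Table 4 (section 8) SUS is again alone in the Fidelity row, with the test given as "Unpaired T-test/ Mann"-Whitney. Section 8 describes all analyses as run "with 95% confidence interval and p < .05 as statistically significant".
- **Qualitative work.** Section 8 also has the core group examine fidelity, feasibility and acceptance by thematic analysis.
- **Data on use.** The eCRF in section 7.a.iii has a block headed Fidelity. It opens with "Total minutes monitored" and goes on to heart-rate and respiratory-rate measurement counts, artefact counts for each, and total spot checks. A separate device block records premature removal and replacement. The text above the eCRF says the additional data serve to relate results to influencing factors and possibly to correct for them.
- **The plan to be delivered.** Section 7.c has every patient admitted to the ward in phase 2 wear the device from intake to discharge, with a reading every 5 minutes.

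**The concern.** Fidelity in the sense of the Summary objective is about delivery: whether patients received the monitoring that was planned, for as long as planned. A usability questionnaire answers a different question, namely what staff think of the system. With SUS > 68 as the only rule, the study could report that its primary fidelity endpoint was met without reporting how many patients were monitored or for what part of their stay. A reader would reasonably take that as evidence of implementation as planned, and the measurement does not support it. The fields that would support or refute it are already in the eCRF under the heading Fidelity, but they have no endpoint, denominator or analysis.

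**Working it through.** The plan states no figure to reproduce: there is no sample-size calculation, no SUS standard deviation and no derivation of the cut-off of 68. The check sets each part of the fidelity definition against what is planned for it.

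**1. Usability.** Instrument: SUS. Criterion: > 68 at month 6. Present in section 7.a.i, Table 2 and Table 4. This half is covered.

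**2. Degree of implementation.** Instrument: none. Criterion: none. Absent from section 7.a.i, Table 2 and Table 4.

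**3. Could SUS stand in for the second half?** The ten items printed in section 11 cover wish to use, complexity, ease, need for help, integration, inconsistency, learnability, awkwardness, familiarity and need to learn more. None asks whether a device was applied, worn or sending data. Write c for monitored time divided by time on the ward. The rule is met if SUS > 68 and not otherwise; c does not enter, so the verdict is the same for c near 0 and c near 1. The unpaired test in Table 4 does not change this: it compares two sets of SUS scores and does not itself test a score against 68.

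**4. Does another planned analysis supply the missing half?**
- The thematic analysis (section 8) addresses fidelity qualitatively and has no criterion.
- Spot checks are analysed, as SC/day (primary) and SC/patient (secondary), but under Acceptance. Section 7.c drops routine manual checks of heart rate and respiration in phase 2, so the count can fall by design without showing that devices were worn.
- The signal-to-noise endpoint concerns false and correct alarms, not wear or coverage.
- Minutes monitored, measurement counts, artefact counts, premature removal and replacement appear in neither table.

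**5. Is there a denominator?** Yes.
- Readings: 24 × 60 / 5 = 288 per parameter per full monitored day, or monitored minutes / 5 for part days.
- Time: the eCRF holds admission and discharge as dates without times. If the dates differ by L days, the true stay lies between L − 1 and L + 1 days, a relative error of up to 1/L. At L = 14 (the approximate battery life in section 7.c) this is 1/14, about 7%; it is larger for shorter stays.

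**6. Precision of a yes/no measure per patient.** The stated turnover of 900 to 1000 a year gives 900/4 = 225 to 1000/4 = 250 patients in three months. Assume that all consent and that the proportion is 80%. The half-width is 1.96 × √(0.8 × 0.2 / n): 0.052 at n = 225 and 0.050 at n = 250, about 5 percentage points. This applies to a share of patients. The precision of a ratio such as monitored minutes over stay depends on a between-patient SD that the documents do not give.

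**7. SUS precision, for completeness.** The number of SUS respondents is not stated. If it were the 15 of the core group, with an assumed SD of 10 to 20, the half-width is t(0.975; 14) × SD / √15 = 2.145 × 10 / 3.873 = 5.5 to 2.145 × 20 / 3.873 = 11.1 points. The point does not depend on this figure.

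**The case against.** The strongest reply has four parts.

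- **SUS measures part of what is defined.** Three of the four statements of fidelity include usability; only the Summary objective speaks of implementation as planned. This stands. A reader might infer that SUS is irrelevant to fidelity, and the documents do not support that: it covers one half.
- **Low use would be seen.** The core group studies fidelity thematically, section 9 adds monthly focus-group evaluation starting after 3 months, and section 6 sets out when a device that fails to connect or measure is exchanged. A reader might infer that the device will hardly be used, or that this would go unnoticed. Neither follows. Section 7.c plans a device for every admitted patient, and low use is only something the rule permits. But none of these safeguards can change the prespecified fidelity verdict. The contra-indications in section 6 also mean that coverage below every admission is foreseeable.
- **The Fidelity block is not wholly unanalysed.** Correct: total spot checks feed the second primary endpoint. The gap concerns the remaining fields.
- **This is a single-ward quality project with mainly descriptive analysis.** That argues for a light remedy. It does not justify a primary success statement that goes beyond its measurement, and no rule requires both primary endpoints to succeed together.

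It is also fair to object that some measures of delivery need data the eCRF lacks. It has no eligibility or contra-indication field and no admission or discharge times, so a share of eligible patients or exact ward minutes cannot be computed from it.

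**Conclusion.** The point holds for the success criterion. Fidelity has two parts by the protocol's own definition, and one has no quantitative measure, threshold or analysis. SUS > 68 supports a statement about usability and none about implementation as planned, whatever the level of device use. The size is a matter of validity rather than precision: one of two primary conclusions does not follow from its measurement. It rests on the wording of the endpoint list, Tables 2 and 4, the SUS items and the eCRF, and needs no assumption about the number of SUS respondents, their SD or the actual level of use. It does not say that use will be low, that SUS has no place in the endpoint, or that nothing in the eCRF Fidelity block is analysed.

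**What to change.** Label SUS > 68 as the usability component only. Add a degree-of-implementation component to the primary fidelity endpoint, computed in phase 2, with rows in Tables 2 and 4 and 95% confidence intervals:

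- (a) share of consenting admitted patients with any monitored minutes;
- (b) monitored minutes per admission divided by length of stay from the admission and discharge dates, stated as accurate only to the day;
- (c) non-artefact heart-rate and respiratory-rate readings divided by those expected in the monitored time (one per 5 minutes, 288 per full day);
- (d) share of patients with premature removal.

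Name one of these, for example (b), as the main measure, and make no claim of implementation as planned from SUS alone. If a success verdict is wanted, the sponsor should set its threshold before the data are examined; the documents give no basis for a value. Two definitions need a line each: what counts as a monitored minute, and whether artefacts are included in the measurement counts.

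Cost: plan wording and a few lines of analysis on fields already collected. A share of eligible patients, or exact ward minutes, would need extra fields (contra-indication, admission and discharge times) and is optional. Downsides: the time denominator is approximate, the data cover consenting patients only, and the fidelity result may look less favourable than a usability score.

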6. INVESTIGATIONAL PRODUCT

a. Name and description of investigational product(s)

The Healthdot is a CE marked wearable data logger (15, 17). It consists of an adhesive layer, electronics and a battery. The intern mechanism contains an accelerometer which is able to measure movement including movement of the lung and heart. This movement data is processed with a validated algorithm to calculate heart rate, respiratory rate, posture and physical activity which are stored on the device and transferred through the LoRa network via the local gateway and/or gateways provided by KPN. The entire technological infrastructure system consists of:

- 1. Healthdot
- 2. Gateway
- 3. KPN-LoRa network
- 4. Server
- 5. Guardian dashboard

Required training

The investigators, nursing staff and physicians will receive a training and e-learning during the pre-implementation phase about the application of the Healthdot, the activation sequence and data reading. In addition, the structure of the study with the questionnaires, the timetable, the procedures in cases of malfunctions/ ADEs will be provided in a protocol.

Contra-indications

- Known to have severe allergy for the tissue adhesive used in the Healthdot.
- Any skin condition, for example prior severe rash, discoloration, scars or open wounds at the area of application
- Pregnant, or breastfeeding
- Use of topical that is known to influence the skin at the test area (such as medical and nonmedical creams or lotions)
- Patient with active implantables such as Implantable Cardioverter Defibrillator (ICD) and pacemaker

SWITCH - Surgical Ward Innovation: Telemonitored controlled by Healthdot

Evaluation of implementation

- Unable to understand instructions
- Left lower rib (place where Healthdot will be applied) is involved in the area of surgery, area of disinfection or area where bandages are needed.
- Transfer to a different ward during hospitalization

Indications for switching Healthdot

- No successful measurement after 4 hours or earlier if clinically necessary.
- When the Healthdot is not connected within 60 min after application

Indications to remove the Healthdot

• In case that an exclusion criterion is met during the study

b. Summary of findings from non-clinical studies

Research into the implementation of a new technology in healthcare can only be investigated in a clinical setting. No non-clinical studies are therefore contributing.

c. Summary of known and potential risks and benefits

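### The 20% spot-check success rule is tied to a count that, read literally, omits the routine checks from the baseline; its windows and its uncertainty also need to be stated

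*Combined protocol and SAP*

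**What the plan says.** **Rule.** The Summary and section 7.a.i set the criterion "Success in case of average reduction of 20% at M6 compared to M3", calculated from the electronic patient file.

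**What is counted.** The Summary's primary objectives give the measure as "Average amount of manual spot checks per hospital admission day". The Summary's endpoint list, section 2 and section 7.a.i instead give "The workload regarding the amount of spot checks in addition to the standard monitoring". Section 7.c describes phase 1 monitoring as "3x daily spot check according to the hospital protocol". In phase 2 the Healthdot is the primary method and its readings are "automatically transferred to the electronic patient file 3 times a day". Nurses do a manual check when one is indicated, and "Additional spot check monitoring for blood pressure, oxygen saturation and temperature may be requested by any member of the treatment team". Section 7.c also says that baseline data on the standard spot-check measurements will be collected. The eCRF list in 7.a.iii holds one spot-check total per admission.

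**When.** The Summary puts phase 1 in months 1–3 and phase 2 in months 3–6. Section 3 and Table 1 put phase 2 in months 4–6, and the measurement timetable (Table 2 in section 3) marks month 4 as the switch. Section 7.c describes a baseline and training phase in months 1–2. The timetable marks the spot-check data under columns 3 and 6, without start or end dates.

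**Analysis.** Table 4 in section 8 lists descriptive statistics for SC/day. A general sentence in section 8 mentions 95% confidence intervals. Section 7.a.iii says results may be corrected for baseline factors.

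**Numbers.** Sections 4.a and 4.d give a turnover of about 900–1000 patients a year. Section 4.d expects no fewer than 500 patients in six months, 250 per phase.

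**The concern.** The standard of care changes at the switch. A count of checks beyond the standard therefore means different things on the two sides of the comparison: in phase 1 it excludes the three routine manual checks, and in phase 2 it includes every manual check. A percentage change between these two quantities does not measure the change in nursing workload, which is the purpose of the endpoint.

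The rule also gives a yes-or-no verdict in an uncontrolled before-after comparison of different patients. If the compared patient-days are not fixed and no interval accompanies the verdict, a reader cannot tell how much of a fall near 20% reflects the choice of window, chance or a change in case mix.

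**Working it through.** The documents give the three protocol checks a day, the 20% threshold and the turnover. They give no expected spot-check rates, no variances and no lengths of stay, so every such value below is an illustrative assumption.

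**1. The plan's own patient number.** Turnover × 6/12, then halved per phase:
- 1000 a year: 500 in six months, 250 per phase, 83 per single month.
- 950 a year: 475, 237.5, 79.
- 900 a year: 450, 225, 75.

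The figure of 500 is reproduced only at the upper end, before any consent refusals.

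**2. The count.** Let x be checks beyond the three protocol checks per patient-day in phase 1 (assumed 0.2 to 0.5), and m manual checks per patient-day in phase 2 (assumed 1.5).

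| | All manual checks | Literal wording |
|---|---|---|
| Phase 1 baseline | 3 + x = 3.2 to 3.5 | x = 0.2 to 0.5 |
| Success if phase 2 is at or below | 0.8(3 + x) = 2.56 to 2.80 | 0.8x = 0.16 to 0.40 |
| Ratio at m = 1.5 | 1.5/3.2 = 0.47; 1.5/3.5 = 0.43 | 1.5/0.2 = 7.5; 1.5/0.5 = 3.0 |
| Result | 53% to 57% reduction | 3.0- to 7.5-fold increase |

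If x = 0, the literal percentage is undefined.

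**3. The window.** Assume 3.0 a day at baseline and 2.7, 2.5 and 2.3 in months 4, 5 and 6, with equal patient-days.
- Month 6 against month 3: 1 − 2.3/3.0 = 23.3% (success).
- Phase against phase: 1 − 2.5/3.0 = 16.7% (failure).

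With 1.7, 1.5 and 1.3 instead, the results are 56.7% and 50.0%, and both succeed. The window decides the verdict only when the fall is near 20%.

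**4. Pooled rate or mean of patient rates.** SC/day (primary) and SC/patient (secondary) are described almost identically. Assume 60 patients staying 3 days at 2.0 checks a day and 20 patients staying 14 days at 2.8, against 3.0 at baseline.
- Pooled: (60×3×2.0 + 20×14×2.8)/(180 + 280) = 2.49, a 17.1% reduction.
- Mean of patient rates: (60×2.0 + 20×2.8)/80 = 2.20, a 26.7% reduction.

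**5. Precision around an observed ratio of 0.80.** SE(log ratio) = √[(1 + CVstay²)(CV1² + CV2²)/n], and the 95% CI is 0.80·exp(±1.96·SE). CV1 and CV2 are the between-patient CVs of the rate in phases 1 and 2. The lower-end n is used: 75 per month and 225 per phase.

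| CV1 / CV2 | CVstay | Single months | Whole phases |
|---|---|---|---|
| 0.2 / 0.6 | 0.5 | 0.68–0.94 | 0.73–0.88 |
| 0.2 / 0.6 | 1.0 | 0.65–0.98 | 0.71–0.90 |
| 0.6 / 0.6 | 0.5 | 0.65–0.99 | 0.71–0.91 |
| 0.6 / 0.6 | 1.0 | 0.61–1.05 | 0.68–0.94 |

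The single-month SE is √3 = 1.73 times the phase SE. These intervals treat patients as independent and ignore ward-level time trends. If the true reduction is exactly 20%, a rule on the point estimate succeeds about half the time.

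**The case against.** The strongest reply is that the protocol answers most of this elsewhere.

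- **Count.** The Summary's objectives name manual checks per admission day, section 7.c includes the standard spot checks in the baseline data, and the eCRF records a total. A reader might infer that the sponsor has left the count open, or that the trial will in fact report a several-fold increase. The documents do not support that: three places point to all manual checks, and the multiples in step 2 depend on assumed rates.
- **Automatic entries.** A reader might also infer that the Healthdot transfers will be counted as spot checks. Nothing proposes this. The measure is manual, and section 7.c describes a phase 2 spot check as done by nursing staff.
- **Window.** Section 3, Table 1 and the timetable agree on a switch at month 4, so the Summary's month 3–6 looks like a slip. The example in step 3 uses rates chosen to straddle 20%.
- **Interval.** The sentence in section 8 covers all analyses, and correction for baseline factors is foreseen. The widest interval in step 5 needs a phase 1 CV of 0.6, which sits poorly with a protocol of three checks a day.
- **Patient number.** The Summary says around 500, and section 4.d disclaims any sample-size calculation, so no power statement depends on it.

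All of this is fair, and it limits the point. What stands is that the conflicting wording sits in the endpoint definition itself, in three places. M3 and M6 are still not defined as months or phases, the interval is not linked to the success rule, and the correction is only a possibility. How a check of only blood pressure, saturation or temperature is counted, and whether patients with a contra-indication to the device are included, are missing details rather than errors.

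**Conclusion.** The endpoint wording in the Summary, section 2 and section 7.a.i is wrong and should be corrected before analysis. Applied literally, the 20% rule would not measure the reduction in workload. On the assumed rates it would turn a 53–57% reduction into a 3.0- to 7.5-fold increase. The intent can be recovered from the rest of the protocol, so this is a correctable drafting error in a decision rule and does not show that the endpoint is unusable.

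The conflict in phase months and the undefined M3 and M6 windows are secondary, because they change the verdict only if the true fall is close to 20%. The missing link between the rule and an interval matters more in an uncontrolled design: with an observed 20% fall, plausible intervals on single months run from roughly 0.65 to 0.98. The minimum of 500 patients is the top of a 450–500 range, which is an editorial correction.

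All rates, CVs and lengths of stay are illustrative. The text conflicts and the turnover arithmetic do not depend on them.

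**What to change.** 1. In the Summary's endpoint list, section 2 and section 7.a.i, define the count as all manual spot checks per patient-day. Include the three protocol checks in phase 1, exclude automatic Healthdot entries, and apply one rule in both phases. State how a partial check is counted. State that SC/day is pooled over patient-days and SC/patient is the mean of patient rates, if that is the intended difference.
2. Reconcile the phase months in the Summary and section 7.c with section 3 and Table 1. State before analysis which patient-days M3 and M6 cover, and report the other window as a sensitivity analysis. Whole phases are more precise but include the first months after the switch. Single months show the settled level with a wider interval.
3. Report the phase 2 to phase 1 rate ratio with a 95% confidence interval beside the 0.80 threshold, with standard errors clustered by patient. A quasi-Poisson model with log patient-days as offset is one suitable choice. Add an estimate adjusted for age, Charlson index, elective or emergency admission and type of surgery. Use dated patient-file records, because the eCRF total per admission cannot split stays that cross the switch.
4. Restate section 4.d as about 450–500 patients (225–250 per phase) before consent refusals.

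**Cost.** Wording changes, a dated export that separates manual from automatic entries, prior coding of two open-text fields (elective or emergency, type of surgery), and a slightly lower expected number. No extra patients or visits are needed. Adjustment for case mix will not remove time trends on the ward, so the before-after limitation remains.
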